Pharmacokinetics: The primary parameters for analysis are area under the concentration versus time curve (AUC) from time zero to infinity ($AUC_{0-\infty}$), AUC from time zero to the time of last measured concentration ($AUC_{0-t_{last}}$), and maximum drug concentration (C_{max}); log transformation will be applied. An analysis of variance model with subject group as fixed factor will be used in the main analyses. The 90% confidence interval of the ratio between each impaired renal function group versus the control group will be estimated. Additional supportive analysis is the evaluation of the relationship between the PK of LY3298176 and mean eGFR, as determined by the Modification of Diet in Renal Disease abbreviated equation. Scatter plots of PK parameter versus eGFR will be produced and analyzed using either a mixed-effects linear or a nonlinear regression approach with eGFR as a continuous covariate on PK parameters.

Safety: Descriptive statistics will be used to summarize safety parameters.

2. Schedule of Activities

Study Schedule Protocol I8F-MC-GPGG

	Screening	Study Days									Follow-up or ED	Comments
Procedure	Days -28 to -1	Day -1	Day 1	Day 2	Day 3	Day 4	Day 5	Day 8	Day 15	Day ≥28		
Informed Consent	X											
Subject Admission to CRU		X										
LY3298176 Administration			X									Study drug will be administered after an overnight fast of at least 8 hours.
Subject Discharge from CRU							X					Subjects may stay longer at the investigator's discretion.
Outpatient Visit								X	X	X		
Medical History	X											
Physical Examination	X	X						X	X	X		After screening, medical assessment only performed to include medical review and targeted examination, as appropriate.
Weight	X	X								X		
Height	X											
Temperature	X	X										
Urine Drug Screen	X	X						X	X			
Ethanol Testing		X						X	X			
Safety 12-lead ECG (hours)	X		Predose		48		X			X		Single ECG will be collected. ECGs must be recorded before collecting any blood samples. Subjects must be supine for approximately 5 to 10 minutes before ECG collection, and remain supine but awake during ECG collection.
Supine Vital Signs (hours)	X	X	Predose, 12	24	48	72	96	168	336	X		Time points may be added, if warranted and agreed upon between Lilly and the investigator.
Clinical Laboratory Tests	X	X			X		X	X	X	X		See Appendix 2 for details.
Estimated Glomerular Filtration Rate	X	X										
Pregnancy Test	X	X						X	X			Female subjects only. See Appendix 2 for details.

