7.2.1. Selection and Timing of Doses

A single dose will be administered by site personnel to each subject in the morning of Day 1. The site of injection administration will be recorded.

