7.8. Treatment after the End of the Study

Not applicable. LY3298176 will not be made available to subjects after conclusion of the study.

8. Discontinuation Criteria

Subjects discontinuing from the study prematurely for any reason must complete AE and follow-up procedures per Section 2 of this protocol.

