8.2. Discontinuation from the Study

Subjects will be discontinued in the following circumstances:

- Enrollment in any other clinical study involving an IP or enrollment in any other type of medical research judged not to be scientifically or medically compatible with this study
- Participation in the study needs to be stopped for medical, safety, regulatory, or other reasons consistent with applicable laws, regulations, and good clinical practice
- Investigator Decision
 - the investigator decides that the subject should be discontinued from the study
 - if the subject, for any reason, requires treatment with another therapeutic agent that has been demonstrated to be effective for treatment of T2DM, discontinuation from the study should occur prior to introduction of the new agent
- Subject Decision
 - the subject requests to be withdrawn from the study
- Adverse event
 - if a clinically significant event (CSE) occurs, the subject is to be discontinued and appropriate measures taken. Lilly or its designee should be alerted immediately. A CSE will be defined as a moderate-to-severe AE, abnormal clinical sign, or clinical laboratory finding that may pose a risk to the well-being of the subject
 - a clinically significant systemic hypersensitivity reaction occurs following administration of the IP (eg, drug-related symptomatic bronchospasm, allergy-related edema/angioedema, or hypotension) that requires parenteral medication, does not respond to symptomatic medication, or results in clinical sequelae or an anaphylactic reaction

- At the discretion of the investigator, if the participant has 2 or more symptomatic hypoglycemic episodes (defined as an event with typical hypoglycemic symptoms and a measured blood glucose ≤ 63 mg/dL [3.5 mmol/L], equivalent to plasma/serum glucose ≤ 70 mg/dL [3.9 mmol/L]; refer to Section 9.4.3)
- Fasting plasma/serum glucose values are >270 mg/dL (approximately 15 mmol/L, equivalent to a fasting blood glucose >241 mg/dL [13.4 mmol/L]) on 3 or more separate days over any 2-week period between screening and the end of the dosing period
- Discontinuation for abnormal pancreatic tests should be considered by the investigator if a subject's lipase and/or amylase are confirmed to be $\geq 3 \times$ ULN. Please refer to the algorithm for the monitoring of pancreatic events in [Appendix 6](#).

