9.4.3.1. Hyperglycemia and Hypoglycemia Reporting

Episodes of hyperglycemia (fasting plasma/serum glucose > 270 mg/dL [15 mmol/L]) or hypoglycemia (plasma/serum glucose ≤ 70 mg/dL [3.9 mmol/L]) will be reported by the investigator or designated physician who will be responsible for advising the subject on what further actions to take. Additional monitoring may be requested at the investigator's discretion.

If the fasting plasma/serum glucose during the dosing period exceeds the acceptable level defined as hyperglycemia on 3 or more separate days over any 2-week period between screening and the end of the dosing period, the subject will be evaluated further at the study site. If fasting plasma/serum glucose continues to exceed the acceptable level, the IP will be discontinued, and treatment with an appropriate antidiabetic agent may be initiated by the investigator. If

hyperglycemia occurs during the follow-up period, the subject will remain in the study until completion of the planned follow-up.

Hypoglycemia episodes will be recorded on specific CRF pages. Hypoglycemia will be treated appropriately by the investigator and additional monitoring of plasma/serum glucose levels may be performed. The following categories of the 2017 American Diabetes Association position statement on glycemic targets (ADA 2017) based on recommendations of the International Hypoglycaemia Study Group (IHSG 2017) should be applied for reporting in the CRF and evaluating hypoglycemic events.

Hypoglycemia will be described using the following definitions:

- **Documented Glucose Alert Level (Level 1), Plasma Glucose (PG) ≤ 70 mg/dL (3.9 mmol/L):**
 - **Symptomatic hypoglycemia:** an event during which typical symptoms of hypoglycemia are accompanied by PG ≤ 70 mg/dL (3.9 mmol/L)
 - **Asymptomatic hypoglycemia:** an event not accompanied by typical symptoms of hypoglycemia but with PG ≤ 70 mg/dL (3.9 mmol/L)
 - **Unspecified hypoglycemia:** an event during which PG ≤ 70 mg/dL (3.9 mmol/L) but no information relative to symptoms of hypoglycemia was recorded
- **Documented Clinically Significant Hypoglycemia (Level 2) PG < 54 mg/dL (3.0 mmol/L):**
 - **Symptomatic hypoglycemia:** an event during which typical symptoms of hypoglycemia are accompanied by PG < 54 mg/dL (3.0 mmol/L)
 - **Asymptomatic hypoglycemia:** an event not accompanied by typical symptoms of hypoglycemia but with PG < 54 mg/dL (3.0 mmol/L)

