9.6.1. Immunogenicity Assessments

For immunogenicity testing, venous blood samples of approximately 10 mL will be collected from each subject according to the Schedule of Activities (Section 2) to determine antibody production against LY3298176. Additional samples may be collected if there is a possibility that an AE is immunologically mediated. All samples for immunogenicity testing should have a time-matched sample for PK analysis. In the event of drug hypersensitivity reactions (immediate or nonimmediate), additional samples will be collected as close to the onset of the event as possible, at the resolution of the event, and 30 days following the event. Instructions for the

collection and handling of blood samples will be provided by the sponsor. The actual date and 24-hour clock time of each sampling will be recorded.

Immunogenicity will be assessed by a validated assay designed to detect ADA in the presence of LY3298176. Antibodies may be further evaluated for their ability to neutralize the activity of LY3298176. Positive LY3298176 ADA samples may also be tested for cross-reactivity with native GLP-1 and GIP, and, if positive, may then be tested for neutralizing antibodies against native GLP-1 and GIP.

All subjects will have an ADA sample measured at early discontinuation or at the follow-up visit. A risk-based approach will be used to monitor subjects who develop treatment-emergent ADA (TE ADA), defined as a titer 2-fold (1 dilution) greater than the minimum required dilution of the assay if no ADA were detected at baseline, or a 4-fold (2 dilutions) increase in titer, compared to baseline, if ADA were detected at baseline.

Clinically significant TE ADA will be defined as any TE ADA at the last visit with:

- a high titer (≥ 1280) or an increasing titer from last measured value
- an association with a moderate-to-severe injection-site reaction or infusion-related reaction
- cross-reactive and/or neutralizing binding of an ADA with endogenous GLP-1 or GIP.

Subjects who have clinically significant TE ADA at early discontinuation or at the follow-up visit should be followed with ADA testing every 3 months for approximately 1 year or until the ADA titers have returned to the baseline ADA titer (defined as ADA titer within 2-fold of baseline). A PK sample may be collected at the follow-up immunogenicity assessment(s), if warranted and agreed upon by the investigator and sponsor.

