Follow this algorithm when the value(s) for serum amylase and/or lipase are $\geq 3 \times$ upper limit of normal.

1. Symptomatic – related to abdominal pain consistent with pancreatitis; however, in the opinion of the investigator, severe nausea and vomiting plus other symptoms consistent with pancreatitis may be considered symptomatic as well.
2. If in the opinion of the investigator, the subject has symptoms of acute pancreatitis:
 - (a) Discontinue subject
 - (b) Consult for assessment and management
 - (c) Assess for causes of pancreatitis
 - (d) Notify Lilly
3. A/L = amylase and/or lipase. Either or both enzymes can be used to meet algorithm criteria.
4. Abdominal imaging is most valuable when performed at the time of elevated enzymes. If, in the opinion of the investigator, it is safe for the subject to receive contrast, and enhanced abdominal CT is preferred. MRI is also an acceptable imaging modality.
5. At a minimum, order a CBC and a pancreatic panel (which includes LFTs, calcium, and triglycerides). Record all concomitant medications

Abbreviations: A/L = amylase and/or lipase; CBC = complete blood count; CT = computed tomography; LFT = liver function tests; MRI = magnetic resonance imaging; ULN = upper limit of normal.

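### Section 8.2 removes a subject from the study after a clinically significant event although the only dose is already given, and the text does not secure that subject's later PK samples

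*Protocol*

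**What the plan says.** Protocol Section 7.2.1: "A single dose will be administered by site personnel to each subject in the morning of Day 1". No further dose is planned.

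Section 8.2, headed as discontinuation from the study, lists the clinically significant event (CSE) among its triggers: "if a clinically significant event (CSE) occurs, the subject is to be discontinued and appropriate measures taken". A CSE is a moderate-to-severe AE, an abnormal sign or a laboratory finding that may put the subject at risk. For symptomatic pancreatitis, Appendix 6 is similar: "If in the opinion of the investigator, the subject has symptoms of acute pancreatitis", the first listed step is to discontinue the subject. Section 8.1 covers only inadvertent enrolment, so it offers no route for staying in the study after an AE.

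Other rules are softer. Repeated hypoglycaemia leads to removal "At the discretion of the investigator, if the participant has 2 or more symptomatic hypoglycemic episodes". For raised glucose after the dosing period, Section 9.4.3.1 takes the opposite line: if "hyperglycemia occurs during the follow-up period, the subject will remain in the study until completion of the planned follow-up".

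The opening of Section 8 says that subjects who leave early "must complete AE and follow-up procedures per Section 2 of this protocol". The Section 2 schedule has separate Day 8 and Day 15 columns. The last visit, Day ≥28, shares a "Follow-up or ED" heading and has one PK sample. On immunogenicity, Section 9.6.1 says: "All subjects will have an ADA sample measured at early discontinuation or at the follow-up visit".

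AUC(0-∞), AUC(0-tlast) and Cmax are the primary parameters. SAP Section 9.3.1 ends AUC(0-tlast) at each subject's own last measurable concentration.

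**The concern.** Stopping a subject usually protects against further exposure. Here no drug remains to be withheld, so removal from the study has no dosing purpose, and what it can cost is data. The 168 h and 336 h PK samples are not preserved by any text. Whether a late sample is taken depends on how a site reads the shared column. The Day ≥28 label points to a sample at that time, but the either/or wording in Section 9.6.1 also fits one sample at removal with nothing after it. Two sites could act differently and both comply.

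The stake is the exposure ratio in groups of about 8 completers. A short profile gives a smaller AUC(0-tlast) for reasons unrelated to clearance. In an impaired group this lowers the ratio to control; in the control group it raises it. The SAP flags AUC(0-∞) when more than 20% is extrapolated, but has no rule specific to a short AUC(0-tlast). Its fixed-time AUC is optional, is triggered only when AUC(0-∞) cannot be determined for all subjects, and could run no later than the shortest profile if it must cover everyone. Replacement under Section 10.1 covers only subjects who were not dosed.

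**Working it through.** **Planning figure first.** Protocol Section 10.1: 16 controls, 8 per impaired group, CV 32%, 90% probability that the 90% CI half-width is within 0.29 (log scale).

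- Half-width = t(0.95, df) × s × √(1/16 + 1/8), and √(1/16 + 1/8) = 0.433.
- With s = 0.32 and df = 22, the chi-square distribution of s² gives P(half-width ≤ 0.29) = 93.4%, and the 90th-percentile half-width is 0.282. Pooled df = 43 gives 98.8%.

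The stated precision is met, so 0.29 is a fair yardstick.

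**Inputs for truncation.**

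- Half-life about 5 days (120 h) and tmax 8–96 h: Protocol Section 3.2.
- Sampling at 0, 8, 12, 24, 48, 72, 96, 168 and 336 h, then follow-up: Section 2. Follow-up is taken as 672 h (Day 28).
- Linear trapezoid to tmax, log trapezoid after: SAP Section 9.3.1.
- Assumed: one compartment, first-order absorption, with ka solved for each tmax of 8, 12, 24, 48, 72 and 96 h.

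**Case 1: ED sample at removal, nothing later.** Let f be the subject's AUC(0-tlast) divided by the full-schedule value. One subject among 8 shifts the group log mean by ln(f)/8, so the ratio is multiplied by f^(1/8). Example: f = 0.421 gives ln(0.421)/8 = −0.108, and exp(−0.108) = 0.897.

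| Last sample | f, tmax 8 h to 96 h | Ratio × | Log shift | Ratio ×, half-life 96–144 h |
|---|---|---|---|---|
| 96 h | 0.421 to 0.240 | 0.90 to 0.84 | −0.11 to −0.18 | 0.83–0.91 |
| 168 h | 0.625 to 0.471 | 0.94 to 0.91 | −0.06 to −0.09 | 0.90–0.96 |
| 336 h | 0.871 to 0.808 | 0.98 to 0.97 | −0.02 to −0.03 | 0.97–0.99 |

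The true extrapolated share of AUC(0-∞) would be 58–77%, 38–54% and 15–22% respectively, against the SAP's 20% flag.

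One truncated control among 16 moves the ratio the other way. For a 96 h last sample, 0.421^(−1/16) = 1.06 and 0.240^(−1/16) = 1.09.

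**Case 2: samples to 96 h plus Day 28.** For tmax 8, 12, 24, 48, 72 and 96 h, f = 1.000, 1.000, 1.000, 0.996, 0.957 and 0.891. The group ratio is multiplied by 1.00 down to 0.891^(1/8) = 0.986. With tmax of 72 or 96 h, only 2 or 1 samples follow tmax (4 or 3 on the full schedule), while SAP Section 9.3.1 wants at least 3 points for the half-life. AUC(0-∞) may then not be estimable. With 3 or more samples after tmax, noise-free AUC(0-∞) is 0.99–1.02 of the truth.

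**SAP outlier rule (Section 9.3.1).** With n ≥ 6, the most extreme log value is compared with mean ± 3 SD of the rest. In a simulation of 8 log-normal values at CV 32%, with one multiplied by f, the truncated value is excluded in about 47–89% of cases for a 96 h last sample and 16–37% for 168 h. If one of 8 drops out, the half-width becomes 0.29 × √(1/16 + 1/7)/√(1/16 + 1/8) = 0.29 × 0.453/0.433 = 0.303.

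**The case against.** The strongest reply is that the protocol does more for these subjects than Section 8.2 suggests.

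- The AE row of the schedule is marked at every visit, Days 8 and 15 included. Section 9.2 has serious, related or discontinuation-causing AEs followed until they resolve, stabilise or are explained. A reader might infer that safety follow-up stops at removal; the documents say otherwise. This stands, but it does not secure the PK draws.
- Hypersensitivity events require ADA samples at onset, at resolution and 30 days later, and Section 9.6.1 wants a time-matched PK sample with each. A late PK sample is therefore specified for that class of event.
- Calling an event a CSE involves judging whether it may pose a risk, and Section 9.4.5 lets the investigator decide on continuation after a significant ECG finding. Removal is less automatic than the sentence sounds. Once an event is judged a CSE, though, the text leaves no option.
- The sizeable effect needs immediate ED with nothing afterwards, and the 0.84 end also needs tmax at 96 h. On the Day ≥28 reading the AUC(0-tlast) effect is negligible.
- The outlier rule would remove many of the worst cases for little loss of precision. It is optional, however, and misses most 168 h truncations.
- The 3-point problem counts only samples after tmax. The SAP does not say whether the peak itself may be used.
- All 23 AEs at 5 mg in the single-dose part of Study GPGA were mild, the interim reviews can cut the dose by about half, and 58 − 48 = 10 extra enrolments are planned.

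These points limit the size of the concern. None of them fills the gap in the wording.

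**Conclusion.** The point holds as a conditional one. Removal after a CSE has no dosing purpose in a single-dose study, and the text leaves open both the Day 8 and Day 15 PK samples and the timing of the last one. The size depends on that timing. With a Day ≥28 sample, AUC(0-tlast) is essentially intact and only AUC(0-∞) with late tmax is at risk. With immediate ED, one subject in 8 shifts the log ratio by up to 0.18 (96 h), 0.09 (168 h) or 0.03 (336 h), all below the planned half-width of 0.29. Cmax is little affected if sampling reaches 96 h. The figures rest on the assumed one-compartment model, a 120 h half-life and one affected subject.

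A reader might go further and infer that the primary comparison will be biased towards no effect, hiding higher exposure in renal impairment. The documents do not support that. They give no CSE rate or timing and no link between CSEs and exposure within a dose, and truncated controls would push the ratio up. This is a cheap improvement to make, not a flaw that undermines the study.

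**What to change.** State in Section 8.2 and Appendix 6 that, after a CSE, a dosed subject who still consents and for whom it is medically acceptable remains in the study for the scheduled Day 8, Day 15 and Day ≥28 PK and safety assessments, whatever clinical action the event requires. Add that an ED visit does not replace the Day ≥28 PK sample. This is the approach Section 9.4.3.1 already takes for hyperglycaemia in follow-up.

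The cost is a wording change and, per affected subject, up to two visits already on the schedule and possibly one extra 3-mL sample. Section 9.5 already permits up to 3 additional PK samples by agreement. Clinical management of the event does not change.

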8.3. Subjects Lost to Follow-up

A subject will be considered lost to follow-up if he or she repeatedly fails to return for scheduled visits and is unable to be contacted by the study site. Site personnel are expected to make diligent attempts to contact subjects who fail to return for a scheduled visit or were otherwise unable to be followed up by the site.

9. Study Assessments and Procedures

Section 2 lists the Schedule of Activities, detailing the study procedures and their timing (including tolerance limits for timing).

Appendix 2 lists the laboratory tests that will be performed for this study.

Appendix 5 provides a summary of the maximum number and volume of invasive samples, for all sampling, during the study.

Unless otherwise stated in subsections below, all samples collected for specified laboratory tests will be destroyed within 60 days of receipt of confirmed test results. Certain samples may be retained for a longer period, if necessary, to comply with applicable laws, regulations, or laboratory certification standards.

9.1. Efficacy Assessments

This section is not applicable for this study.

9.2. Adverse Events

Investigators are responsible for monitoring the safety of subjects who have entered this study and for alerting Lilly or its designee to any event that seems unusual, even if this event may be considered an unanticipated benefit to the subject.

The investigator is responsible for the appropriate medical care of subjects during the study.

Investigators must document their review of each laboratory safety report.

The investigator remains responsible for following, through an appropriate health care option, AEs that are serious or otherwise medically important, considered related to the IP or the study, or that caused the subject to discontinue the IP before completing the study. The subject should be followed until the event resolves, stabilizes with appropriate diagnostic evaluation, or is reasonably explained. The frequency of follow-up evaluations of the AE is left to the discretion of the investigator.

After the informed consent form is signed, study site personnel will record, via CRF, the occurrence and nature of each subject's preexisting conditions, including clinically significant signs and symptoms of the disease under treatment in the study. Additionally, site personnel will record any change in the condition(s) and the occurrence and nature of any AEs.

The investigator will interpret and document whether or not an AE has a reasonable possibility of being related to study treatment or a study procedure, taking into account the disease, concomitant treatment, or pathologies.

A "reasonable possibility" means that there is a potential cause and effect relationship between the IP, study device, and/or study procedure and the AE.

Planned surgeries should not be reported as AEs unless the underlying medical condition has worsened during the course of the study.

9.2.1. Serious Adverse Events

An SAE is any AE from this study that results in one of the following:

- death
- initial or prolonged inpatient hospitalization
- a life-threatening experience (ie, immediate risk of dying)
- persistent or significant disability/incapacity
- congenital anomaly/birth defect
- important medical events that may not be immediately life threatening or result in death or hospitalization but may jeopardize the subject or may require intervention to prevent one of the other outcomes listed in the definition above.

Study site personnel must alert the Lilly CRP/CP, or designee, of any SAE as soon as practically possible.

Additionally, study site personnel must alert Lilly Global Patient Safety, or its designee, of any SAE within 24 hours of investigator awareness of the event via a sponsor-approved method. If alerts are issued via telephone, they are to be immediately followed with official notification on study-specific SAE forms. This 24-hour notification requirement refers to the initial SAE information and all follow-up SAE information.

Although all AEs are recorded in the CRF after signing informed consent, SAE reporting to the sponsor begins after the subject has signed informed consent and has received IP. However, if an SAE occurs after signing informed consent, but prior to receiving IP, AND is considered Reasonably Possibly Related to a study procedure then it MUST be reported.

Investigators are not obligated to actively seek AEs or SAEs in subjects once they have discontinued from and/or completed the study (the subject summary CRF has been completed). However, if the investigator learns of any SAE, including a death, at any time after a subject has been discharged from the study, and he/she considers the event Reasonably Possibly Related to the study treatment or study participation, the investigator must promptly notify Lilly.

Pregnancy (maternal or paternal exposure to IP) does not meet the definition of an AE. However, to fulfill regulatory requirements any pregnancy should be reported following the SAE process to collect data on the outcome for both mother and fetus.

